Breast cancer survivors are living longer and quality of life, including sexual health, is important. Females with estrogen deficiencies may suffer from vaginal dryness and atrophy that negatively impact sexual health. Chemoprevention treatment with Als blocks estrogen production and compounds the problem. Vaginal DHEA, a non-estrogen product, is known to improve vaginal atrophy and sexual health. This study will evaluate the use of vaginal DHEA in breast cancer survivors on Als.

Objectives and Rationale

The primary objective is to determine change in vaginal atrophy as assessed by the VMI after 12 weeks (± 1 week) of treatment with vaginal DHEA 6.5 mg inserted nightly (Intrarosa®) when compared to a prefilled applicator of a polycarbophil vaginal moisturizing gel (6.7 g) (Replens™), into the vagina two times per week at night.

The secondary objectives are to 1) determine change in vaginal pH 2) determine improvement of vaginal symptoms and sexual function as assessed by the Brief Sexual Symptom Checklist for Women (BSSC-W) and the Female Sexual Function Index (FSFI) [10-11] and 3) determine improvement in quality of life using the Quality of Life - Cancer Survivor Version (QOL-CSV) [12] after 12 weeks (±1 week) of treatment with vaginal DHEA (Intrarosa[®]) when compared to polycarbophil vaginal moisturizer (Replens™) in breast cancer survivors on AI, and to compare side effects in each group that may impact patient acceptability.

It is hypothesized that the Intrarosa[®] arm will exhibit greater improvement in the VMI and decrease in vaginal pH when compared to Replens[™] after 12 weeks (±1 week) of treatment. It is also hypothesized that the Intrarosa[®] arm will have improvement in vaginal and sexual symptoms as indicated by the validated symptom inventories to be administered both pre and post study period.

Of note, the BSSC-W, the FSFI, and the QOL-CSV have all been validated for use in a study population such as this one [10-12].

IRB 239531 Sponsor: UAMS Version 15 0/7/07/2023 Page 6 of 22

Study Population

Subjects will be postmenopausal breast cancer survivors, stage I-III, hormone receptor positive breast cancer (ER+, PR+) regardless of human epidermal growth factor receptor 2 (HER2) status, ages 18 to 70 years old, on Als identified at UAMS Cancer Institute and Women's Health clinics and at CARTI Cancer Center. Up to 120 subjects will be screened for a total of 60 subjects enrolled, 30 in each arm of the study. See Appendix B.

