• If at any point it is discovered that the subject has missed ≥25% of the total prescribed treatment doses (21 doses of Intrarosa® or 6 doses of Replens™).

Risks and Benefits

Although prior trials have not reported serious physical side effects with DHEA, there is a risk of possible side effects from DHEA. The most significant side effect reported in prior studies was an increase in vaginal discharge, reported in 6% of users [14-15]. In an extended 52-week trial, changes in Pap smear were reported in 2.1% (11 of 521) subjects. None of the reported abnormal Pap results were high-grade lesions [14-15]. During the final gynecologic exam, a Pap smear may be done at the treating physician's discretion if abnormal cervical changes are suspected.

IRB 239531 Sponsor: UAMS Version 15 0/7/07/2023 Page 11 of 22

Intrarosa® package insert lists the following adverse reactions from clinical trials experience [6]:

- Vaginal discharge (incidence of ≥ 2%, and greater than reported in the placebo group)
- Abnormal Pap smear (incidence of 2.1%)

Under a "warnings and precautions" section, the package insert lists "current or past history of breast cancer," noting that exogenously-administered estrogen is contraindicated in females with history of breast cancer, and that estrogen is a metabolite of prasterone. Additionally, it states, "Intrarosa® has not been studied in women with breast cancer." [6] However, since publication of the package insert in 2016, high-quality studies have concluded that serum estrogen and testosterone concentrations were maintained in the normal postmenopausal ranges in breast cancer survivors on Al's after extended use of Intrarosa® [7,13,16] mitigating concern for this subgroup, who are the focus of the study proposed here.

There is a risk of minor discomfort with the pelvic exams proposed in this study. Subjects will undergo a physical exam outside of the scheduled visits if a subject experiences distress from side effects she perceives to be resulting from the study treatment.

There is a risk of psychological distress due to subjects filling out questionnaires about sexual health and quality of life. These questionnaires will be assessed and subject's feelings about sexual health and quality of life will be monitored for the duration of the study.

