An event is "related" if more likely than not it was caused by the research activity.

IRB 239531 Sponsor: UAMS Version 15 0/7/07/2023 Page 13 of 22

Unexpected

An event is "unexpected" when its specificity, nature, severity, or incidence is not accurately reflected in the consent form, protocol, or investigator's brochure previously reviewed and approved by the IRB. Examples include a lower rate of response to treatment or a side effect that is more severe than initially expected.

Study Period

Following consent (i.e. study entry), baselines/pre-existing conditions will be assessed until initiation of study treatment. All AEs will then be recorded through the end of the designated follow-up period (i.e. week 12, ±1 week). All AEs will be recorded within the research database AR-Adverse Events Reporting System (AR-AERS).

Abnormal Laboratory Values Defined as AEs

An abnormal laboratory value is considered an AE if the laboratory abnormality is characterized by any of the following, for test done as part of the research protocol:

- Results in discontinuation from the study
- Requires treatment, modification of study treatment dose, or other therapeutic intervention
- Is judged by the Investigator to be of significant clinical impact/importance
- Grade 3 or Grade 4 lab abnormalities regardless of significance

If a laboratory abnormality is one component of a diagnosis or syndrome, then only the diagnosis or syndrome should be recorded as an AE. If the laboratory abnormality was not a part of a diagnosis or syndrome, then the abnormality should be recorded as the AE.

Estradiol levels will be measured at baseline and 12 weeks (±1 week) from Day 1, Week 1 of treatment. A report will be sent to FDA for any subject with an estradiol level out of the normal postmenopausal range at 12 weeks (±1 week) from Day 1, Week 1 of treatment.

Monitoring, Recording and Reporting of AEs

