Protocol violation: a change to, or non-compliance with the IRB-approved procedures without prior Sponsor and IRB approval. Violation may affect health, safety, or rights of a subject. Any violation will be reported immediately to the Sponsor for guidance on reporting. Violations will be made available for Monitors to check against source data at each monitoring visit.

If the protocol deviation/protocol violation does not represent a significant alteration in the approved protocol and/or affect the safety or welfare of the subject, it will be reported to the UAMS IRB at the time of Continuing Review. If the protocol deviation or protocol violation represents a significant alteration in the approved protocol and/or if it affects the safety or welfare of the subject, it must be reported to the UAMS IRB immediately.

Compliance

All drug boxes and unused product will be collected from subject at last visit by research staff and will be given to the research pharmacy to log for compliance. No serious harm is anticipated from non-adherence or cessation of use of the investigational products.

Subject Withdrawal

Subjects may withdraw from treatment or consent from the study at any time for any reason, without penalty.

Subjects who voluntarily withdraw from study treatment will stop taking the study drug but will still participate in the research-related assessments. These research-related assessments include physical exam (including clinical breast and gynecological exam for pH and VMI), estradiol level, completion of BSSC-W, QOL-CSV, and FSFI, and reporting of AEs until the end of the study duration [i.e., Week 12 (±1 week)].

Subjects who withdraw consent from the study will stop taking the study drug and all research-related assessments will be ceased. Any data previously collected will be used but no further data will be collected following the subject's withdrawal of consent. Subjects will be encouraged to report AEs thought to be possibly/probably related to the study drug for 30 days after discontinuation.

For evaluation and reporting purposes, reasons for early withdrawal may be discussed with willing subjects for purposes of identifying potential problems with the drug or study design. When possible, subjects will be notified that any improvement in symptoms they perceived to be the

IRB 239531 Sponsor: UAMS Version 15 0/7/07/2023 Page 17 of 22

result of the study intervention may recede and a return to the pre-study baseline can be expected.

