The efficacy population will include all subjects with a baseline assessment who have received at least two weeks of treatment with either Intrarosa® or Replens™. Subjects who discontinue participation in the study (stop the assigned treatment, withdraw consent, etc.) before 2 weeks of treatment will not be included in the efficacy population. Subjects who discontinue participation in the study after 2 weeks but prior to 12 weeks will be included in the efficacy analysis. These subjects will be invited to complete the end of study evaluation at the time of discontinuation; these evaluation values will be included in the efficacy analyses.

The safety population will include all subjects who received at least one administration of either Intrarosa® or Replens™.

Efficacy Endpoints

The primary efficacy endpoint is VMI Response, which is defined as the change in the subject's calculated VMI from baseline to the end of treatment at 12 (±1 week).

Secondary efficacy endpoints: Secondary efficacy endpoints for all study subjects will be determined both at baseline and at the end of treatment. They consist of the following:

- Vaginal pH
- Dyspareunia and vaginal dryness scores on the BSSC-W and the FSFI,
- Quality of life using the QOL-CSV.

IRB 239531 Sponsor: UAMS Version 15 0/7/07/2023 Page 18 of 22

Analysis Plan

Descriptive Analysis: Each efficacy endpoint will be summarized by treatment group and time point as the mean, standard deviation (SD), minimum, 1st quartile, median, 3rd quartile, and maximum. Within each subject, the endpoint's response to treatment will be defined (and calculated) as the endpoint's value at 12 weeks minus its value at baseline; the resulting endpoint responses will be summarized by treatment group as the mean, SD, minimum, 1st quartile, median, 3rd quartile, and maximum. Graphical displays will consist of box plots and scatter plots along with profile plots, a.k.a. "spaghetti plots", that show how the individual subjects respond over time to their assigned treatment. Adherence to distributional assumptions will be assessed, and data transformation to increase such adherence will be implemented, if warranted.

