i Gynecologic exam, including vaginal pH and VMI activities can take place on the same day as consent and Day 1, Week 1 as long they are completed after consent, all other eligibility criteria have been met, and prior to Day 1, Week 1 activities. SoC breast and pelvic exams may be used if completed within 28 days of Day 1, Week 1.

j During the gynecologic exam, a Pap smear may be performed at the treating physician's discretion if abnormal cervical changes are suspected.

k If the VMI results are "unsatisfactory", the swab of vaginal epithelium will need to be recollected within 4 weeks of Day 1, Week 1 to calculate a new VMI.

A report will be sent to FDA for any subject with an estradiol level out of the normal postmenopausal range at week 12 (±1 week).

m All AEs reported during clinic visits, on diaries, by phone or email, etc. are to be documented, assessed by the PI or designee, and tabulated.

n Diary progress should be submitted after Week 4 (±1 week), Week 8 (±1 week) of treatment. Diaries can be submitted in person, via self-addressed envelope to CTO, text photos to the research nurse cellphone, email photos to the research nurse email, sent photos through MyChart, or faxed to CTO. There will be no deviation for subjects who do not submit diary progress at Week 4 or Week 8.

o Diary progress should be submitted after Week 12 (±1 week) of treatment, or end of treatment. Diaries can be submitted in person, via self-addressed envelope to CTO, text photos to the research nurse cellphone, email photos to the research nurse email, sent photos through MyChart, or faxed to CTO. There will be a deviation for subjects who do not submit diary progress at Week 12 or if they come off treatment early.

Follow-up call should occur at 1 week ±3 days after Day 1, Week 1.

q Follow-up call should occur at 6 weeks ±1 week after Day 1, Week 1.

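### Estradiol is collected at baseline and Week 12 in both arms, but no summary by arm or of change is planned, so a group-wide rise that stays inside the postmenopausal range could go unseen

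*Combined protocol and SAP*

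**What the plan says.** **Collection.** Under Abnormal Laboratory Values Defined as AEs: "Estradiol levels will be measured at baseline and 12 weeks". The Study Calendar (Appendix A) marks estradiol at baseline and at end of treatment, for both arms. Under Subject Withdrawal, women who stop the study drug but keep their consent still give "estradiol level, completion of BSSC-W, QOL-CSV, and FSFI, and reporting of AEs until the end of the study duration".

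**The estradiol rule.** The same laboratory section states: "A report will be sent to FDA for any subject with an estradiol level out of the normal postmenopausal range at 12 weeks". An Appendix A footnote repeats it: "A report will be sent to FDA for any subject with an estradiol level out of the normal postmenopausal range at week 12". Neither place gives numeric limits or a direction, and neither refers to the baseline value.

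**Other criteria that apply.** The laboratory section also makes an abnormal value an adverse event if it leads to discontinuation, needs treatment or a dose modification, is Grade 3 or 4, or "Is judged by the Investigator to be of significant clinical impact/importance".

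**Analysis.** The primary endpoint is change in VMI. The secondary list, introduced by "Secondary efficacy endpoints for all study subjects will be determined both at baseline and at the end of treatment", holds vaginal pH, dyspareunia and dryness scores, and quality of life. The descriptive analysis covers efficacy endpoints, and so do the tests. The planned safety analysis is a tabulation of adverse events by organ system. A safety population is defined, but no laboratory analysis is attached to it.

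**Context.** Background and Rationale says that treatment with aromatase inhibitors "blocks estrogen production and compounds the problem". Risks and Benefits relays the label warning, including "that estrogen is a metabolite of prasterone".

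**The concern.** Every woman in the trial has been on an aromatase inhibitor for at least 6 months, so her baseline estradiol reflects blocked production. The informative question is whether Intrarosa moves estradiol from that level, compared with Replens. A Week-12 check against a range for postmenopausal women does not ask this. The baseline sample that would allow it has no stated analytic use, and neither does the randomized control.

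The protocol supports use of the drug in these women by pointing to hormone levels that stayed within the normal postmenopausal ranges. A report that no subject was out of range would be read as further support, yet the plan provides no estimate of a shift within subjects or between arms. The trial is open-label, so an estradiol analysis chosen after the data are seen would carry less weight than one written down now.

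**Working it through.** **Step 1. Reproduce the plan's own figure.** Sample Size and Power holds the only design calculation: 0.8 SD in VMI response at one-sided α = 0.05. No figure is given for estradiol. The formula is power = 1 − F(t₀.₉₅; df, δ), where F is the noncentral t distribution, df = 2n − 2 and δ = d√(n/2).

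- n = 30 per arm: δ = 0.8 × √15 = 3.10, power 92.2% (stated 92.2%).
- n = 24 per arm: δ = 0.8 × √12 = 2.77, power 86.1% (stated 86.1%).
- Wilcoxon, with n scaled by 0.955: 91.1% and 84.6% (stated 91.2% and 84.9%).

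The plan's figures hold, so the same method is used below.

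**Step 2. What the planned numbers could show for estradiol.** Use two-sided α = 0.05 to match a two-sided 95% CI. Solve the power formula, with t₀.₉₇₅, for 80%. The CI half-width is t₀.₉₇₅ × √(2/n).

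- n = 30 per arm: detectable shift 0.74 SD; half-width 2.00 × 0.258 = 0.52 SD.
- n = 24 per arm: detectable shift 0.83 SD; half-width 2.01 × 0.289 = 0.58 SD.

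The unit is the SD of the change being compared. The documents give no SD for estradiol.

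**Step 3. When a range check misses a rise.** The following are assumptions, none of them in the documents: lognormal values, CV 50% to 100%, within-subject correlation 0.5, and an upper limit U of 2, 4 or 10 times the median on an aromatase inhibitor. Then σ = √ln(1 + CV²) = 0.472 to 0.833. For a true f-fold rise, P(flag) = 1 − Φ(ln(U/f)/σ). With U = 10, f = 2 and CV 50%, for example, ln 5/0.472 = 3.41, which gives 0.03%.

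| U | P(flag), no rise | P(flag), true doubling | Expected flags in 30, true doubling |
|---|---|---|---|
| 2 | 7% to 20% | 50% | 15 |
| 4 | 0.2% to 5% | 7% to 20% | 2.1 to 6.1 |
| 10 | under 0.3% | 0.03% to 2.7% | 0.01 to 0.8 |

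**Step 4. The same doubling, analysed as log change between arms.** The SD of log change is σ√(2(1 − 0.5)) = σ. A doubling is therefore 0.693/0.472 = 1.47 SD or 0.693/0.833 = 0.83 SD. Two-sided power is above 99% (CV 50%) or 89% (CV 100%) with 30 per arm, and above 99% or 81% with 24. This does not depend on U. For a 1.5-fold rise, power is 90.5% or 45.8% with 30 per arm, and 82.9% or 37.9% with 24.

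**Step 5. Step 2 as ratios, under the same assumptions.** The detectable ratio with 30 per arm is exp(0.736 × 0.472) = 1.42 to exp(0.736 × 0.833) = 1.85. The 95% limits lie a factor of exp(0.517 × 0.472) = 1.28 to exp(0.517 × 0.833) = 1.54 either side of the estimate.

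These t-based figures do not apply if many values fall below the assay limit.

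**The case against.** The strongest reply has three parts. The quoted sentence is an FDA reporting trigger, not a statistical decision rule. The postmenopausal range is the benchmark the protocol uses throughout, and whether it suits these women is a clinical judgement. The protocol also cites studies in women on aromatase inhibitors as mitigating the concern, and names vaginal discharge as the most significant reported side effect. All of this stands, and it is why the trigger should be left alone and why the point should not be called the trial's main safety question. None of it supplies an analysis of the paired samples.

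Four stronger readings are tempting, and the documents do not support them.

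- *Estradiol is judged solely by the range.* The general laboratory criteria also apply. What is true is that they rest on grade, judgement or action taken, not on change from baseline or a comparison of arms.
- *A woman already out of range at baseline would be reported as a new case.* Monitoring, Recording and Reporting of AEs treats laboratory abnormalities present at baseline as pre-existing, and nothing says that the FDA report would label the value as new.
- *The range rule cannot detect a shift.* With a limit at twice the on-inhibitor median, a doubling would be expected to flag 15 of 30 women. The documents do not give the assay, the limits or the on-inhibitor levels that decide this.
- *The upper bound after zero flags measures the defect.* With 0 of 30 flagged the one-sided 95% bound is 1 − 0.05^(1/30) = 9.5% (11.7% with 24). That holds for any yes/no outcome and says nothing about range against change.

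A practical objection also stands. Not every subject will have a Week-12 value, since withdrawal of consent ends assessments and termination can end participation. Women who stop the drug but stay on study would also dilute a comparison of arms.

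**Conclusion.** The point holds in a limited form. Paired estradiol data are collected in both randomized arms, and the plan neither summarises nor compares them. That gap is read directly from the documents and needs no assumption.

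That a group-wide rise could stay inside the range is a possibility, not a finding. Under the assumptions shown, the chance that a subject is flagged after a true doubling runs from 50% to 0.03%, depending mainly on where the limit lies. A between-arm comparison of log change would detect the same doubling with at least 89% power at 30 per arm, but a 1.5-fold rise with only 46% power if the CV is 100%. The added analysis is therefore more informative than the range check alone, but it is estimation and could not show absence of effect. The primary VMI analysis is not affected. This is an inexpensive improvement that is worth making.

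**What to change.** Leave the FDA report unchanged. Add a safety analysis to the Analysis Plan, for treated subjects with estradiol data:

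- **Summaries by arm** of baseline, Week-12 and within-subject change in estradiol, with the number of subjects missing a Week-12 value.
- **Between-arm comparison** of Week-12 log estradiol by ANCOVA adjusted for baseline log estradiol, reported as a ratio with a two-sided 95% CI. If many values are below the assay limit, use a rank-based or censored-data method, and say in advance which one and when.
- **Sensitivity analysis** limited to subjects still on treatment at Week 12.
- **Out-of-range counts** by arm at both baseline and Week 12.

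Record the assay, its quantification limit and the range the laboratory applies, so that the counts can be interpreted. State that the analysis is safety estimation outside the alpha plan, and that a confidence interval including 1 is not evidence of no effect.

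The cost is some SAP wording, one table and one model on data already collected. No new sample, visit or subject is needed. The drawback is one more reported comparison, which the safety label and the interval-based reporting keep in proportion.

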Primary Efficacy Analyses: To determine each treatment arm's VMI response to treatment, the Intrarosa® arm will be compared to the ReplensTM arm for the difference in their VMI responses using Student's t-test if group variances are equal, Welch's t-test if group variances are unequal, or Wilcoxon's rank-sum test if data violate normality assumptions. In keeping with the research hypothesis that the Intrarosa® arm will exhibit greater improvement in the VMI when compared to the ReplensTM arm after 12 weeks (± 1 week) of treatment, this primary-efficacy comparison will be conducted using a one-sided test at an $\alpha = 0.05$ significance level to look specifically for increased VMI response in the Intrarosa® arm. The follow-up of this primary-efficacy comparison will be analyzed using an ANCOVA model that has 12-week VMI as the outcome variable, treatment arm as the factor of interest, and baseline VMI as the continuous covariate.

Secondary Efficacy Analyses: For each secondary endpoint, the treatment arms will be compared for a difference in the endpoint at baseline, a difference in the endpoint at 12 weeks (± 1 week), and a difference in the endpoint's response to treatment. All comparisons will be conducted using 1-sided tests that employ a multiple-comparison-adjusted $\alpha = 0.01$ significance level to look specifically for improvements with Intrarosa® compared to Replens™. The tests will consist of Student's t-test, Welch's t-test, or Wilcoxon's rank-sum test depending on the endpoint's adherence to distributional assumptions. In follow-up analysis, each secondary endpoint will be analyzed using an ANCOVA model that has the endpoint's 12-week value as the outcome, treatment arm as the factor of interest, and endpoint's baseline value as the continuous covariate.

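### The primary analysis mixes exit-visit VMI with a 12-week endpoint and drops subjects who stop before 2 weeks, with no efficacy analysis of all randomised subjects

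*Combined protocol and SAP*

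**What the plan says.** **Endpoint.** Efficacy Endpoints defines VMI Response as the change in the "calculated VMI from baseline to the end of treatment at 12" (±1 week). The Descriptive Analysis paragraph computes each endpoint's response as the "value at 12 weeks minus its value at baseline". The follow-up to the primary comparison is an "ANCOVA model that has 12-week VMI as the outcome variable". Footnote c of the study calendar (Appendix A) places the End of Treatment visit at Week 12 (±1 week) from Day 1.

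**Stoppers after 2 weeks.** Efficacy and Safety Populations keeps them in the efficacy analysis. They are "invited to complete the end of study evaluation at the time of discontinuation; these evaluation values will be included in the efficacy analyses".

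**Stoppers before 2 weeks.** The efficacy population is "all subjects with a baseline assessment who have received at least two weeks of treatment". Of subjects who discontinue early, the section says: "stop the assigned treatment, withdraw consent, etc.) before 2 weeks of treatment will not be included in the efficacy population". The only other set defined is the safety population.

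**Follow-up after stopping.** Under Subject Withdrawal: "Subjects who voluntarily withdraw from study treatment will stop taking the study drug but will still participate in the research-related assessments". Those assessments include VMI and run to Week 12 (±1 week).

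**Missing values.** MAR, MCAR and MNAR are in the abbreviation list, but the Data Analysis section states no missing-data method and no sensitivity analysis.

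**The concern.** Two separate matters affect the primary comparison.

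The first is which VMI is analysed. The endpoint is fixed at 12 weeks, but the population rule admits a value taken at any time after 2 weeks. A voluntary stopper may have both an exit value and a Week-12 value, and the plan does not mention the second when it says what enters the analysis. The exit visit is by invitation, and nothing is said about a subject who declines it.

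The second is who is analysed. Completing 2 weeks of treatment happens after randomisation. Subjects know whether they have a nightly insert or a twice-weekly gel, so who reaches 2 weeks may depend on the arm. The groups compared need not then be the groups randomised. Blinded cytology protects the reading of the smear, not the selection of subjects. Voluntary early stoppers would still attend at Week 12, so the rule leaves out data that the trial plans to collect.

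At stake are the meaning of the primary estimate and, if exclusions are both unbalanced and related to response, the one-sided 5% error rate.

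**Working it through.** **1. The plan's own figures.** Inputs from Sample Size and Power: effect 0.8 SD, one-sided α = 0.05, Student's t-test, 30 or 24 per arm. The noncentrality is 0.8 × √(n/2), with 2n − 2 degrees of freedom.
- n = 30: 0.8 × √15 = 3.10, critical t(58) = 1.672, power 92.2%.
- n = 24: 0.8 × √12 = 2.77, critical t(46) = 1.679, power 86.1%.

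Both match the plan.

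**2. Timing.** The window opens at 12 − 1 = 11 weeks. An exit value may date from just after 2 weeks, so the gap is up to 11 − 2 = 9 weeks.

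**3. Excluding early stoppers when there is no true difference.** The documents give no number of early stoppers, no split by arm and no response data for them, so these inputs are assumed. Suppose k of 30 Intrarosa subjects and none on Replens are excluded, and the excluded subjects' mean response is δ SD below that of the other Intrarosa subjects. The arm's overall mean is zero, so the retained mean is (k/30) × δ. The noncentrality is that shift × √[(30 − k) × 30 / (60 − k)], with 58 − k degrees of freedom.

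Example, k = 3 and δ = 1.0: shift 0.10 SD; 0.10 × √(27 × 30 / 57) = 0.377; critical t(55) = 1.673; rejection rate 10.2%.

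| Excluded (Intrarosa only) | 0.5 SD lower | 1.0 SD lower | 0.5 SD higher | 1.0 SD higher |
|---|---|---|---|---|
| 1 | 5.7% | 6.4% | 4.4% | 3.8% |
| 2 | 6.4% | 8.2% | 3.8% | 2.9% |
| 3 | 7.2% | 10.2% | 3.4% | 2.2% |

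With 3 Intrarosa and 1 Replens excluded, all lower, the net shift is (3/30 − 1/30) × δ and the rate is 6.4% (δ = 0.5) or 8.1% (δ = 1.0). With equal numbers and the same δ in both arms the shifts cancel; simulation of 1-3 per arm gives 5.0-5.1%.

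**4. Exit value in place of Week-12 value.** Suppose k of 30 Intrarosa subjects stop and their exit and Week-12 values differ on average by c SD (assumed). The estimated difference moves by (k/30) × c.
- k = 6, c = 0.4: 0.08 SD.
- k = 3, c = 0.4: 0.04 SD.
- c = 0: no shift.

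The sign can go either way. For scale, the critical difference at 30 per arm is 1.672 × √(2/30) = 0.43 SD. A shift of ±0.08 SD moves power at 0.8 SD to 95.8% or 86.7%. Under a true null, +0.08 SD gives noncentrality 0.08 × √15 = 0.310 and a 9.0% rejection rate.

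**5. Power if all randomised subjects are analysed at Week 12.** Assume k of 30 Intrarosa subjects stop and keep a fraction r of the 0.8 SD effect. The mean difference is 0.8 × [1 − (k/30)(1 − r)]. Power is simulated (400,000 runs, Student's t, 30 per arm, every Week-12 value available).

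| Stoppers | r | Mean difference (SD) | Power |
|---|---|---|---|
| 6 (20%) | 0 | 0.64 | 77.7% |
| 6 (20%) | 0.25 | 0.68 | 82.5% |
| 6 (20%) | 0.5 | 0.72 | 86.4% |
| 3 (10%) | 0 | 0.72 | 86.2% |
| 3 (10%) | 0.25 | 0.74 | 88.0% |
| 3 (10%) | 0.5 | 0.76 | 89.7% |

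**The case against.** The strongest defence is that the rules are prespecified and identical in both arms. A minimum-exposure analysis set is common in Phase II, and making an all-randomised set primary is partly a choice of estimand. For a stopper, the exit visit is in a natural sense the end of treatment. Both values exist only for a voluntary stopper who accepts the exit visit and also returns at Week 12.

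The routes to exclusion before 2 weeks are also limited. The cumulative missed-dose limit (21 Intrarosa or 6 Replens doses) cannot be reached in 14 nights, which hold 14 or 4 doses. Three related Grade 3 or higher events across the arms end the study, so that route cannot supply three exclusions in a continuing trial. The 10.2% figure needs three exclusions in one arm, none in the other, and a full 1 SD deficit.

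Much of this stands, and it lowers the rating. It does not remove the point. Voluntary stops, lower-grade events and the consecutive-miss rule can still lead to exclusion before 2 weeks. The end-of-treatment reading conflicts with the three places that name 12 weeks and with the calendar footnote. Prespecifying a post-randomisation exclusion does not make the comparison randomised.

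A reader might infer more than the documents support:
- *That a subject with both values has no defined response.* The population section does include the exit value. The gap is that it is silent on whether the Week-12 value replaces it.
- *That the power calculation is wrong.* It reproduces, and the subjects remaining after 20% attrition can fairly be read as those with evaluable VMI.
- *That a missing-at-random method is ruled out because the effect fades off drug.* The documents give no off-drug course for VMI; the statement in Subject Withdrawal that improvement may recede concerns perceived symptoms.

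**Conclusion.** The point holds on the text. The analysis admits VMI from just after 2 weeks into an endpoint defined at 11-13 weeks, does not say whether an available Week-12 value takes precedence, and excludes randomised subjects on a post-randomisation criterion with no all-randomised efficacy analysis beside it.

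It would be tempting to conclude that the plan favours Intrarosa. The documents do not support that: they give no VMI time course, no rate of early stopping by arm and no responses for stoppers. Under the assumed inputs the error rate runs from 2.2% to 10.2%, and stays at about 5% if exclusions are balanced. The exit-value shift runs from zero to 0.08 SD in either direction. The case rests on a consistently defined endpoint and a randomised comparison, not on a demonstrated bias. Rating: SHOULD-FIX.

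**What to change.** - **Primary analysis:** all randomised subjects in their assigned arm, using VMI at Week 12 (±1 week) whether or not drug was stopped.
- **Precedence:** where exit and Week-12 values both exist, use the Week-12 value. Use exit values only in a sensitivity analysis or as auxiliary information when Week-12 VMI is missing.
- **Secondary analysis:** keep the current 2-week population and exit-value rule, labelled as on-treatment.
- **Missing Week-12 VMI:** prespecify one method and a sensitivity analysis. The choice of method can be left to the sponsor's statistician.
- **Separately, reconcile two pairs of passages.** Efficacy and Safety Populations invites subjects who withdraw consent to an exit evaluation, while Subject Withdrawal ends data collection for them. Dosing Delays makes termination for missed doses mandatory, while Subject Termination leaves termination for not following procedures to the investigator. No clinical rule is proposed here.

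**Cost.** This is amendment wording plus one missing-data paragraph; the Week-12 visit for voluntary stoppers is already scheduled. Subjects terminated by the investigator or withdrawing consent may have no Week-12 value and would fall under the missing-data rule. The primary estimate would include subjects off drug, so power may fall below 92.2%: to about 78-86% if 20% of the Intrarosa arm stop and keep 0-50% of the effect (assumed).
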